## 3.3 Masking

Treatment administration will not be masked. Trial images will be uploaded to the Reading Center (RC) and evaluated there by graders masked as to treatment assignment. All other assessments will be made using unmasked examiners.

## 4.0 Outcomes

#### 4.1 Primary Outcome

The primary outcome of the ADVISE Trial will be a corticosteroid-sparing treatment success, defined as inactive uveitis, on prednisone  $\leq$ 7.5 mg/day for 2 consecutive visits  $\geq$ 28 days apart within the first 6 months after randomization with individuals as the unit of analysis. The 2 consecutive visits  $\geq$ 28 days apart was used in the SITE Cohort Study to avoid overestimation of benefits among participants who transiently achieve corticosteroid-sparing, but promptly relapse at the next visit. Since a minimum of two follow-up visits must occur prior to achieving a corticosteroid sparing success and prednisone must be tapered, the first outcome evaluation will occur at 2 months (V03) and will continue at every visit until the final study visit at 12 months (V10).

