# 3.3 Trial schematic

# 3.4 Outcomes

# 3.4.1 Primary outcome

The primary outcome of the ADVISE Trial will be a corticosteroid-sparing treatment success, defined as inactive uveitis, on prednisone  $\leq$ 7.5 mg/day for 2 consecutive visits  $\geq$ 28 days apart within the first 6 months after randomization. The SITE Cohort Study required 2 consecutive visits  $\geq$ 28 days apart to avoid overestimation of benefits among patients who transiently achieve corticosteroid-sparing, but promptly relapse at the next visit. We will use a similar methodology for the same reasons. The prednisone taper schedule used in the ADVISE Trial (see Table 4 in section 4.2.2) is designed to permit clear evaluation of this outcome.

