### 4.2.1 Initial prednisone dose

• Patients with active uveitis not on prednisone:

The initial dose of prednisone is the maximum allowed dose (i.e., 1 mg/kg/day up to a maximum of 60 mg/day) for 2 weeks. Prednisone tapering will be initiated at 2 weeks per section 4.2.2 if the uveitis is controlled. If the study ophthalmologist expects the uveitis to be controlled within 2 weeks, the prednisone tapering may be initiated automatically at 2 weeks without a clinic visit. Should uveitis fail to be controlled after 2 weeks or if the study ophthalmologist did not expect it to be controlled within 2 weeks, the maximum allowed dose will be continued for 2 additional weeks (total of 4 weeks). To avoid complications of systemic corticosteroid therapy, after 4 weeks of prednisone at the maximum allowed dose, prednisone tapering will be initiated per section 4.2.2. If the uveitis is neither controlled nor substantially improved such that it is expected to be inactive by next visit (V03 in 4 weeks), then, immunosuppression will be advanced per section 4.4. Additional advancement of the immunosuppressive treatment will be implemented according to guidelines in section 4.4 until inflammation is controlled or else the best medical judgment point of guidelines is reached.

- Patients already on prednisone with a reactivation of uveitis:

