# 4.2.2 Prednisone tapering schedule and goals

After initially obtaining (or maintaining) quiescence of uveitis with treatment(s) or when the prednisone dose has been used for the maximum duration described in section 4.2.1,

prednisone will be tapered as described in Table 4 below, starting from the dose of corticosteroids they begin tapering from.

- The primary outcome of the trial is a prednisone dose of ≤7.5 mg/day for 2 visits ≥ 28 days apart with inactive uveitis. If a patient is begun on prednisone 60 mg/day, the primary outcome should be reached by 15 weeks of follow-up.
- If a patient achieves the primary outcome, an attempt should be made to taper further and discontinue prednisone. A range of tapering decrements for prednisone doses below 7.5 mg/day is necessary due to the need to taper prednisone more slowly among those already on long-term oral corticosteroid therapy to minimize corticosteroid-withdrawal symptoms but still permit discontinuation by 1 year of follow-up.
- The prednisone dose should not be tapered below 7.5 mg/day if the patient has active uveitis unless required according to best medical judgement.
- If uveitis reactivates during tapering, follow the guidelines for prednisone dosing in the reactivation management guidelines in section 4.5.

Table 5. Prednisone tapering schedule						
Dose (mg/day)	Interval (decrease every)					
60 to 30	10	1 week				
30 to 15	5	1 week				
15 to 7.5	2.5	1 week				
7.5 †	Hold at 7.5 mg/day until two study visits ≥ 4 weeks (28 days) apart have occurred*					
<7.5 †	1-2.5	2 weeks				

\*Note: This may involve maintaining the dose for more than two consecutive study visits if they occur <28 days apart.

† Do not taper below 7.5 mg/day until uveitis is inactive

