# 4.8 Ancillary therapy

# 4.8.1 Regional corticosteroid Injections

The MUST Trial demonstrated that the majority of patients with uveitic macular edema require supplemental regional corticosteroid injections (either periocular or intravitreal) to improve the macular edema, but that they typically need only one or two injections. Therefore, participants in the ADVISE Trial with uveitic macular edema will be permitted a regional corticosteroid injection within the first 2 months, if needed, and a second injection during months 6 to 8 (if needed) for persistent macular edema (to meet patients' clinical needs without contaminating key outcomes). Acceptable regional injections are: 1) periocular triamcinolone acetonide 40 mg, 2) intravitreal triamcinolone acetonide 4 mg (Triesence® [Alcon Laboratories, Inc., Fort Worth, TX] preferred if available due to its being preservative free for intravitreal use).or 3) the dexamethasone intravitreal pellet (Ozurdex ®, Allergan, Inc., Irvine, CA). If a participant is given an injection during the first 2 months of the trial, the dose of prednisone should not go below 7.5 mg/day (or if already <7.5 mg/day, should not be tapered further) until 3 months after the injection, as the primary outcome only can be ascertained 3 months after an injection. Allowing the limited use of regional corticosteroid injections for uveitic macular edema is necessary for proper clinical care, and the restrictions on their use will permit evaluation of the trial's outcomes.

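### A primary-outcome success can be scored and fixed within three months of a regional corticosteroid injection, when the Protocol says the outcome cannot be ascertained

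*SAP*

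**What the plan says.** **Injections.** Under Protocol 4.8.1, participants with uveitic macular edema "will be permitted a regional corticosteroid injection within the first 2 months, if needed", with a second possible in months 6 to 8. After an injection in the first two months, "the dose of prednisone should not go below 7.5 mg/day" "until 3 months after the injection, as the primary outcome only can be ascertained 3 months after an injection". Someone already under 7.5 mg/day is not tapered further during that time.

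**Definition.** Protocol 3.4.1 reads: "The primary outcome of the ADVISE Trial will be a corticosteroid-sparing treatment success, defined as inactive uveitis, on prednisone" of at most 7.5 mg/day, at two consecutive visits at least 28 days apart within 6 months. SAP 4.1 repeats it. Neither mentions injections.

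**Derivation.** SAP 4.1 says that "the first outcome evaluation will occur at 2 months (V03) and will continue at every visit" up to V10. SAP 6.3 analyses the cumulative proportion and treats a success as permanent.

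**Taper.** Protocol 4.2.2 says that from 60 mg/day "the primary outcome should be reached by 15 weeks of follow-up". Its tapering table adds "Hold at 7.5 mg/day until two study visits" at least 28 days apart have taken place.

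**Elsewhere in the SAP.** Ocular corticosteroid injections appear only in SAP 6.4, as an example of a repeated event. SAP 6.7 deals with missed visits and loss to follow-up, not with visits that took place but cannot be used.

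**The concern.** A programmer who follows the SAP will count visits that the Protocol says cannot support the primary outcome. One who follows Protocol 4.8.1 will not. The same data can therefore give two primary results.

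The two-visit rule is there to keep out transient successes. The Protocol's version 1.3 revision note puts the effect of the dexamethasone pellet at about three months, similar to intravitreal triamcinolone, which is long enough to span two monthly visits. Because a success is never reversed, a later relapse cannot undo it. Treatment and clinical activity assessment are unmasked (Protocol 3.1, SAP 3.3), so injection use could differ between arms. The interim efficacy test and the 5% non-inferiority fallback in SAP 7.1 use the same outcome.

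**Working it through.** **1. The plan's 15 weeks.** The Protocol 4.2.2 taper has 3 weekly steps from 60 to 30 mg, 3 from 30 to 15 and 3 from 15 to 7.5, which is 9 steps. Two weeks at 60 mg + 9 weeks + a 4-week hold = 15 weeks, as stated. The 7.5 mg dose is reached at week 10 or 11, depending on whether the first cut falls at week 2 or week 3.

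**2. Visits.** On calendar months V03, V04, V05, V06 and V07 fall at about weeks 8.7, 13.0, 17.4, 21.7 and 26.1. Protocol 4.2.1 counts four weeks between V02 and V03, in the phrase "expected to be inactive by next visit (V03 in 4 weeks". On that spacing the same visits fall at weeks 8, 12, 16, 20 and 24. Either way, a dose of 7.5 mg reached at week 10 or 11 makes V04/V05 the first possible pair.

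**3. Window laid over the visits** (window end = injection month + 3, nominal months):

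| Injection month | Window ends | Visits inside, to V07 | Pairs after the window, by V07 |
|---|---|---|---|
| 0 | 3 | V02, V03 | V04/V05, V05/V06, V06/V07 |
| after 0, up to 1 | after 3, up to 4 | V02*, V03, V04 | V05/V06, V06/V07 |
| after 1, up to 2 | after 4, up to 5 | V03*, V04, V05 | V06/V07 |

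*Only if the injection came before that visit's assessment.

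For an injection after month 1 and up to month 2, V04 and V05 are both inside.

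**4. Lower starting doses.** A participant on 10 mg/day who tapers at week 4 needs one step and reaches 7.5 mg at week 4 or 5, so V03/V04 can qualify. V04 is inside the window for any permitted injection after baseline.

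**5. The floor.** It forbids going below 7.5 mg/day. The limit for success is 7.5 or less, so a participant held at the floor is at a qualifying dose.

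**6. Who is classified differently.** Under the SAP, any qualifying pair by V07 is a success. Under Protocol 4.8.1, the pair may not use an in-window visit. Take an injection at month 1.5, with inactive uveitis on 7.5 mg/day at V04 and V05 and active uveitis at V07. The SAP fixes a success at V05. Under 4.8.1 only V06/V07 is left, and it fails. A participant inactive on 7.5 mg/day or less through V07, with V06 and V07 clear of the window and at least 28 days apart, succeeds under both rules.

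**7. Size.** 1/111 = 0.0090, or 0.9 percentage points per net participant reclassified in one arm.

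**8. Illustration only.** Let a share q of each arm be injected, and let a share r of injected would-be failures gain a success solely from an in-window pair. The difference then shrinks by q × r × (0.75 − 0.5125), where 0.5125 = 0.75 × 0.55 + 0.25 × 0.40 (SAP 6.2 gives 51%). For q = 10% and r = 5% this is 0.12 points; for q = 30% and r = 50% it is 3.56 points. Both shares are assumptions.

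**9. Limits of the remaining pair.** On four-week visits V03 is day 56 and V06 is day 140. Two calendar months run to about day 61, so an injection on days 57 to 61 leaves only 83 to 79 days before V06, less than the 84 days between V03 and V06. V06 and V07 are then exactly 28 days apart, and a 27-day gap would not qualify.

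**The case against.** The strongest reply is that the sentence in Protocol 4.8.1 explains a dosing floor and is not a scoring rule, and that macular edema is not scored as activity (Protocol 3.4.3, 4.1). But the sentence speaks of when the primary outcome can be ascertained, and the floor does not deliver that.

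The affected group is also narrow: macular edema, an early injection, a qualifying pair in the window and none outside it. That stands, and it limits the point. SAP 6.3 plans component and duration-of-success analyses, SAP 5.0 a per-protocol analysis and SAP 6.4 a comparison of repeated-event rates. These could expose such cases but leave the primary result unchanged. The Manual of Procedures, which holds the criteria for inactive uveitis, was not available and may contain a rule. Neither document cites it for this purpose.

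Three stronger readings are tempting, and the documents support none of them:

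- *Every in-window success is false.* For an injection at month 2, the holds in Protocol 4.2.2 and 4.8.1 can both have ended by V06. A relapse at V07 may therefore occur on a lower prednisone dose.
- *The bias favours one arm.* No figures on injection use by arm are given.
- *Power falls to about 80%.* The extreme corner of the illustration takes power from 89.9% to 79.8% (111 per arm, 10% loss counted as failure, two-sided 0.0492). It needs 30% injected and 50% converting, and it needs the planned 51% and 75% to exclude in-window successes. The documents state none of these.

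**Conclusion.** The conflict is real and should be fixed. Followed as written, the SAP scores visits that Protocol 4.8.1 says cannot establish the primary outcome, and it then makes the result permanent. The exposure lies on the expected path: V04/V05 from 60 mg/day, and V03/V04 from lower doses.

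The consequence cannot be sized beyond 0.9 points per net reclassification. Protocol 4.8.1 says that most patients with uveitic macular edema need such injections, but it does not say how many trial participants will have the condition. The conclusion rests on visits near their nominal times and on there being no scoring rule in the Manual of Procedures. Confidence is medium.

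**What to change.** Before the interim analysis, reconcile Protocol 4.8.1 with Protocol 3.4.1 and SAP 4.1 and 6.3. For the 6-month primary outcome, state that:

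- visits after a regional corticosteroid injection and within 3 months of it do not count toward the success pair, and a pair may not bridge them;
- visits up to and including the assessment at the injection visit still count;
- the rule covers any such injection before V07, on schedule or not;
- the 3 months are a number of days with a stated visit tolerance;
- a participant with no evaluable pair by V07 is classified in a specified way. A late month-2 injection, an early V06 or a V06/V07 gap under 28 days can each cause this.

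Pre-specify the unrestricted definition as a sensitivity analysis. Report by arm how many participants are injected and how many change status. If the sponsor prefers unrestricted scoring for the primary analysis, the documents should say so and the sentence in 4.8.1 should be reconciled with it.

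The sponsor should also reconcile the holds at 7.5 mg/day in Protocol 4.2.2 and 4.8.1 with the timing of the evaluable pair. No dose or clinical rule is proposed here.

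The cost is some wording, one programmed rule and one further analysis; the sample size does not change. The injection dates should be available, since SAP 6.4 already plans to model these events. The downsides are slightly lower success rates, a few participants without an evaluable pair, and some injected participants judged later than uninjected ones.

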## 4.2 Secondary Outcomes

Secondary outcomes will include data collected at all follow-up visits, i.e. V02-V10, according to the collection schedule presented in Table 1.

- Secondary corticosteroid sparing outcomes:
  - Corticosteroid-sparing success: The ability to achieve inactive uveitis and prednisone <7.5 mg/day for 2 consecutive visits >28 days apart within one year of randomization
  - Prednisone discontinuation success: The ability to achieve inactive uveitis and discontinue prednisone for 2 consecutive visits >28 days apart within one year of randomization
  - Prednisone exposure (e.g. cumulative prednisone dose and/or mean prednisone dose) in the two groups through 1 year of follow-up.
- Best corrected visual acuity measured after a standardized refraction using logarithmic visual acuity charts
- Incidence of infections
  - Any infections requiring antimicrobial therapy
  - Tuberculosis (clinical diagnosis of tuberculosis)
  - o Invasive fungal infections
  - o Dermatomal or disseminated herpes zoster
- Macular edema measured using Optical Coherence Tomography (OCT)
- Quality of life (QoL) data collected at baseline, 3, 6, and 12 months
  - Health utility (EuroQoL 5-dimension [5D] and visual analog scales)
  - General health assessment (SF-36)
  - Vision related QoL (the 25-item National Eye Institute Visual Function Questionnaire [NEI-VFQ-25])
- Safety outcomes:
  - Systemic adverse events (e.g. cytopenias, elevated creatininte, elevated liver enzymes)
  - Serious adverse events (e.g. death, life-threatening adverse drug experience, inpatient hospitalization or prolongation of existing hospitalization)

#### 5.0 Analysis Populations

The primary analyses will be based upon the 'as randomized' population, i.e. individuals will be included in the analysis according to their assigned treatment regardless of the actual treatment received, which follows the principle of intention to treat (ITT). A number of sensitivity analyses based upon the treatment received will be explored including but not limited to the following two examples. First, an 'as treated' analysis will incorporate individuals according to the current treatment received, which may change over time. Second, a 'per protocol' analysis will limit the analysis to the subset that received the assigned treatment according to the guidelines of the protocol throughout follow-up. Additional sensitivity analyses using causal inference techniques will be considered to address the issues of confounding and treatment by indication that arise from analyses based upon treatment received.

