# 3.7 Data collection schedule

Participants will be followed monthly for 6 months, and every two months thereafter until anniversary study closeout 1 year after randomization. The visit and examination schedule is given in Table 2.

Table 3. Visit and examination schedule										
Month	BL*	1	2	3	4	5	6	8	10	12
Visit ID	V01	V02	V03	V04	V05	V06	V07	V08	V09	V10
All patients										
Visual acuity †	Х	Х	Х	Х	Х	Х	Х	Х	Х	Х
Medical, ophthalmic, and treatment history	Х	Х	Х	Х	Х	Х	Х	Х	Х	Х
Weight and blood pressure	Х	Х	Х	Х	Х	Х	Х	Х	Х	Х
Height	Х									
Eye examination	X	Х	Х	Х	Х	Х	Х	Х	Х	Х
Optical coherence tomography (OCT) +	Х			Х			Х			X
Retinal color photographs ‡	X	V	V	V	V	V	X	V	V	X
Complete blood count & chemistry panel 	X	Х	Х	X	Х	Х	X	Х	Х	X
Quality of life (EuroQoL, SF-36, NEI-VFQ)	X			Х			Х			Х
Disease-specific tests										
Disease Test(s)										
Birdshot chorioretinitis Visual field ¶	Х	Х	Х	Х	Х	Х	Х	Х	Х	Х
Choroiditis (all except birdshot) FAF ∥	Х	Х	Х	Х	Х	Х	Х	Х	Х	Х
VKH, early disease OCT ^	Х	Х	Х	Х	Х	Х	Х	Х	Х	Х
VKH, late disease FAF	Х	Х	Х	Х	Х	Х	Х	Х	Х	Х
Retinal vasculitis and FA #	Х	Х	Х	Х	Х	Х	Х	Х	Х	Х
panuveitis with retinal vasculitis										
Tests to identify exclusion characteristics										
prior to enrollment										
Interferon-y release assay for tuberculosis	Х									
(all patients)**										
Hepatitis B panel % ;hepatitis C antibody (all)	Х									
Gadolinium enhanced MRI for patients with	Х									
anterior/intermediate or intermediate uveitis										
without systemic disease only ††										
Pregnancy test for women of child bearing	Х									
potential										
* BL = baseline		.								
† Evaluation of best corrected visual acuity after st	andard	refracti	on							
 UCT centered on tovea  9 field 50 or 60° photographs or wide field photog	aranh (e		tos)							
§ Including creatinine liver enzymes and serum du	ucose	.g., op	103)							
¶ Either quantitative Goldmann perimetry or autom	nated pe	rimetry	with H	lumphr	ev SIT.	A-fast 3	30-2 ar	nd Scre	ening	P60
may be used, but once chosen, the visual field test	ing shou	uld be t	he san	ne for a	all visit t	for eac	h indivi	idual pa	atient	
FAF= fundus autofluorescence										
^ OCT centered on fovea & additionally, as needed	d, OCT (	centere	d to ca	pture a	area wi	th grea	itest su	bretina	l thickr	iess

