Although it might be argued that conventional immunosuppressive agents might be used initially at the maximum dose to avoid the dose escalation step, this alternative approach does not mimic clinical practice, whereas the use as outlined in Table 5 does. Furthermore, this approach minimizes the possibility of drug-related side effects, and many patients respond to the initial dose without need for dose escalation. For example, among patients who respond to treatment with methotrexate, the majority do so at a dose of 15 mg/week. For patients assigned to conventional immunosuppression requiring changes in the immunosuppressive agent for side effects, an attempt will be made (if possible) to change within class (e.g., a different antimetabolite); if not possible, the alternative class may be used, or if necessary best medical judgment. These guidelines are presented in more detailed outline format in the Manual of Procedures section 8.5.

If uveitis reactivates after achieving prednisone cessation, prednisone will be reinstated at a dose of at least 10 mg/day up to the maximum allowed dose (i.e., 1 mg/kg/day if < 60 kg or 60 mg/day if  $\ge$  60 kg), depending on the severity of the reactivation. The study physician will determine whether to advance immunosuppression per best medical judgment.

Table 6a. Reactivation management guidelines: Prednisone							
Scenario	Action for prednisone dose	First opportunity to taper	Second opportunity to taper				
		(2 weeks after prednisone increase)*	(4 weeks after prednisone increase)				
Reactivation during prednisone taper	If current dose ≥ ½ maximum allowed dose, increase to maximum allowed dose If current dose < ½ maximum allowed dose, increase to between double current dose and maximum allowed dose depending on severity	Controlled: Taper Not controlled: If increased dose is not maximum allowed dose, increase to maximum allowed dose	Controlled: Taper Not controlled: Taper but not below 7.5 mg/day until uveitis is inactive				
Reactivation after tapered off prednisone	Reinitiate prednisone at dose of at least 10 mg/day up to the maximum allowed dose (i.e., 1 mg/kg/day if < 60 kg or 60 mg/day if $\ge$ 60 kg), depending on the severity of the reactivation	Controlled: Taper Not controlled: Treat per best medical judgment	Controlled: Taper Not controlled: Treat per best medical judgment				

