#### 6.3 Primary outcome analysis

The primary goal of the trial is to establish whether adalimumab is superior to conventional immunosuppression for corticosteroid-sparing in the treatment of individuals with intermediate, posterior, or pannuveitis. The analysis will focus on the cumulative proportion with a success. Once a success has been achieved, then it will remain fixed for that individual thereafter. A more standard time to event analysis, which allows for censoring due to loss to follow-up, was considered. However, because the time required to taper prednisone to  $\leq 7.5$  mg/day depends substantially on the initial prednisone dose, small imbalances at baseline could influence greatly such analyses despite stratification. Therefore, time to event analyses will be used as sensitivity analyses. The 6-month time frame was chosen to allow sufficient time to observe the primary outcome regardless of the participant's prednisone dose at randomization and is likely to be more robust to imbalances. Multiple imputation will be used to address missing data due to missed interim visits and loss to follow-up.

Since a minimum of two follow-up visits must occur prior to achieving a corticosteroid success and prednisone must be tapered, the first outcome evaluation will occur at 2 months (V03) and will continue for every visit thereafter. Modeling will focus upon the period between 6 months and 1 year due to the potential for imbalances in the tapering patterns described above. Generalized estimating equations (GEE) will be used to fit logistic regression models comparing the two treatment groups over time while accounting for the correlation between replicate measurements. A saturated mean structure including visits starting at 6 months (V07-V10), treatment, and visit by treatment interaction terms plus the two stratification variables (baseline immunotherapy and initial prednisone dose) will be used. The mean model structure is:

$$logit(Y) = \beta_0 + \beta_1 A + \beta_2 P + \beta_3 S + \beta_4 V_7 + \beta_5 V_8 + \beta_6 V_9 + \beta_7 V_{10} + \beta_8 I_7 + \beta_9 I_8 + \beta_{10} I_9 + \beta_{11} I_{10}$$

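### The per-protocol sensitivity set is defined by adherence to month 12, so for the 6-month outcome it excludes patients for deviations that occur after that outcome is settled

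*SAP*

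**What the plan says.** SAP 5.0 makes the intention-to-treat comparison primary: "The primary analyses will be based upon the 'as randomized' population, i.e. individuals will be included in the analysis according to their assigned treatment". It then adds supporting work: "A number of sensitivity analyses based upon the treatment received will be explored including but not limited to the following two examples". The second example is the per-protocol analysis, restricted to the "subset that received the assigned treatment according to the guidelines of the protocol throughout follow-up". No other per-protocol set is defined, and none is tied to a visit. The section closes by saying that "Additional sensitivity analyses using causal inference techniques will be considered to address the issues of confounding and treatment by indication", without specifying a method.

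The timing comes from other sections. SAP 4.1 places the primary outcome "within the first 6 months after randomization with individuals as the unit of analysis". SAP 6.3 says of the outcome: "Once a success has been achieved, then it will remain fixed for that individual thereafter". Protocol 3.7 sets the length of follow-up: "Participants will be followed monthly for 6 months, and every two months thereafter until anniversary study closeout 1 year after randomization". Protocol 3.4.2 treats the 1-year visit as the end of follow-up, and Protocol 4.3.1 continues adalimumab to that point. Read with these, the adherence window in SAP 5.0 runs to month 12.

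**The concern.** A patient can follow the assigned regimen to V07, have the 6-month outcome recorded, and depart from the protocol guidelines at month 9. The outcome cannot change, yet the SAP 5.0 wording removes the patient from a per-protocol comparison at month 6. Membership of the set thus depends on events after the endpoint.

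This matters if late departures are related to whether the patient had succeeded by month 6. That is plausible. Patients with persistent or recurrent activity move up the advancement steps of Protocol 4.4 and 4.5 towards best medical judgment, and 6-month failures are more likely to be among them. If the proportions excluded also differ by arm, the per-protocol difference may grow, shrink or appear without a true difference, for reasons unrelated to treatment in the first 6 months. Treatment and clinical assessment are unmasked, so readers will want an analysis by treatment received as a check on robustness. A distorted version could falsely contradict or falsely support the primary result.

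**Working it through.** **1. The plan's own figure.** SAP 6.2 gives stratum shares of 75% and 25%, conventional success rates of 55% and 40%, adalimumab success of 75%, and 10% loss counted as failure.

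- Conventional: 0.75 × 0.55 + 0.25 × 0.40 = 0.5125 (stated as 51%); 0.5125 × 0.9 = 0.461.
- Adalimumab: 0.75 × 0.9 = 0.675.
- Power with 111 per arm, pooled variance under the null: z = [√111 × 0.214 − 1.96 × √(2 × 0.568 × 0.432)] / √(0.461 × 0.539 + 0.675 × 0.325) = (2.255 − 1.373) / 0.684 = 1.29, which gives 90.1%.
- At the final-analysis level of 0.0492 in SAP 7.1, power is 90.0%.

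The stated 90% reproduces. It belongs to the as-randomized comparison and does not involve the per-protocol set. The documents give no size for that set and no deviation rate, so no per-protocol figure can be reproduced.

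**2. Formula for the illustration.** Let p be the true 6-month success rate in an arm, and let s and f be the proportions of 6-month successes and failures excluded for deviations in months 7–12. Then

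per-protocol rate = p(1 − s) / [p(1 − s) + (1 − p)(1 − f)].

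The values p = 0.51 (conventional) and 0.75 (adalimumab) are the plan's. All values of s and f are assumptions.

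**3. Results with the planned rates (true difference 24.0 points).**

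| Assumed exclusion | Conventional | Adalimumab | Difference (points) |
|---|---|---|---|
| 10% or 20% of everyone, unrelated to outcome | 51.0% | 75.0% | 24.0 |
| s = 5%, f = 20% in both arms | 55.3% | 78.1% | 22.8 |
| s = 5%, f = 40% in both arms | 62.2% | 82.6% | 20.4 |
| s = 5%; f = 40% conventional, 10% adalimumab | 62.2% | 76.0% | 13.8 |
| s = 5%; f = 10% conventional, 40% adalimumab | 52.4% | 82.6% | 30.3 |

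As an example, the conventional rate in the fourth row is 0.51 × 0.95 / (0.51 × 0.95 + 0.49 × 0.60) = 0.4845 / 0.7785 = 62.2%. In the first row only numbers fall, from 111 to about 100 or 89 per arm.

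**4. No true difference.** With both arms at 51%, s = 5%, and f = 10% in one arm and 40% in the other, the rates are 52.4% and 62.2%. That is a spurious difference of about 10 points, in favour of whichever arm loses more failures. If s and f are equal in the two arms, equal true rates stay equal.

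**5. Would ending each patient's window at first success do instead?** It would not. Suppose that true success is 60%, successes occur at month 4, failures are followed to month 6, and deviations are unrelated to outcome at 3% or 10% per month (all assumed).

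- At 3%: 0.6 × 0.97⁴ / (0.6 × 0.97⁴ + 0.4 × 0.97⁶) = 0.531 / 0.864 = 61.5%.
- At 10%: 0.6 × 0.9⁴ / (0.6 × 0.9⁴ + 0.4 × 0.9⁶) = 0.394 / 0.606 = 64.9%.

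Successes are exposed to exclusion for a shorter time than failures, so this rule selects on outcome even when deviations do not.

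**The case against.** The strongest reply is that nothing decisive rests on this set. A reader might infer from the wording that the 6-month primary comparison is itself restricted. It is not: SAP 5.0 and Protocol 8.3 base it on assigned treatment. The per-protocol analysis is one of two examples of exploratory work, and the superiority test, the interim stopping rule and the power are not tied to it. This stands, and it limits the severity.

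A second reply is that one set covering all of follow-up suits a model fitted jointly to V07–V10, and suits the 1-year outcomes. That is a fair reason for a month-12 set at 1 year. It does not justify using month-12 adherence for the V07 contrast.

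Third, the SAP acknowledges confounding in analyses by treatment received. But causal methods are only to be considered, and the exclusion rule stays as written.

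Fourth, it is not certain whom the rule removes. Advancement under the guidelines is not a deviation, and best medical judgment is itself a protocol step. The SAP does not say how such treatment, or stopping for toxicity or pregnancy, is classed. This stands: only changes that fall outside the guidelines would exclude a patient.

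A reader might also infer a built-in asymmetry. Protocol 4.5 describes drug substitution for side effects in the conventional arm, and no replacement for adalimumab is described. But Protocol 4.7.1 on stopping for toxicity covers both arms, and Protocol 4.5 also sends conventional patients to best medical judgment if necessary. The documents do not establish which arm would lose more patients, so they do not fix the direction of any bias.

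**Conclusion.** The point holds for the per-protocol sensitivity analysis of the 6-month outcome. Followed exactly, SAP 5.0 excludes patients for deviations after that outcome is fixed. The as-randomized estimate and its 90% power are unaffected.

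The size cannot be taken from the documents. Under the assumed exclusion rates, the planned 24-point difference lies between 13.8 and 30.3. Two equal arms can appear about 10 points apart. If late deviations are unrelated to 6-month success, the difference stays at 24.0 and only precision is lost. These results rest on reading the adherence window as 12 months, which the other sections support, and on exclusion rates that are illustrative.

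A reader might set the spurious 10 points against the 5% non-inferiority margin in SAP 7.1. That section names no analysis population, so the documents do not show that the per-protocol set would be used there. Severity: minor.

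**What to change.** In SAP 5.0, define the per-protocol set by analysis time point, with the same fixed window for every participant: randomization through V07 for the 6-month outcome, and randomization through V10 for the 1-year outcomes. Do not end the window at first success, for the reason shown in step 5 of the working. Where V07–V10 are modelled jointly, fit the V07 contrast on the V07 set. State one classification rule, applied identically in both arms, for substitutions under Protocol 4.5, discontinuations under Protocol 4.7 and treatment by best medical judgment.

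The cost is a few lines of SAP text, one derived adherence flag per time point, and per-protocol sets that differ between 6 months and 1 year.
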